Active joint count	Change from baseline of active joint count	ITT	Week 2 to Week 16	Summary statistics mBOCF for missing post-baseline values
		OLE	Week 16 to Week 104	Summary statistics mBOCF for missing post-baseline values
		OLE Switcher	Week 16 (or Switch to IXE) to Week 104	Summary statistics mBOCF for missing post-baseline values
Limited of range motion joint count	Change from baseline of limited range of motion joint count	ITT	Week 2 to Week 16	Summary statistics mBOCF for missing post-baseline values
		OLE	Week 16 to Week 104	Summary statistics mBOCF for missing post-baseline values
		OLE Switcher	Week 16 (or Switch to IXE) to Week 104	Summary statistics mBOCF for missing post-baseline values
Physician's global assessment of disease activity	Change from baseline of physician's global assessment of disease activity	ITT	Week 2 to Week 16	Summary statistics mBOCF for missing post-baseline values

Measure	Variable	Population	Analysis Timepoint	Analysis Method
		OLE	Week 16 to Week 104	Summary statistics
				mBOCF for missing post-baseline values
		OLE Switcher	Week 16 (or Switch to IXE) to Week 104	Summary statistics
				mBOCF for missing post-baseline values
Physical function as measured by CHAQ	Change from baseline of physical function	ITT	Week 2 to Week 16	Summary statistics
				mBOCF for missing post-baseline values
		OLE	Week 16 to Week 104	Summary statistics
				mBOCF for missing post-baseline values
		OLE Switcher	Week 16 (or Switch to IXE) to Week 104	Summary statistics
				mBOCF for missing post-baseline values
Parent's global assessment of overall well-being as measured by CHAQ	Change from baseline of parent's global assessment of overall well-being	ITT	Week 2 to Week 16	Summary statistics
				mBOCF for missing post-baseline values
		OLE	Week 16 to Week 104	Summary statistics
				mBOCF for missing post-baseline values
		OLE Switcher	Week 16 (or Switch to IXE) to Week 104	Summary statistics
				mBOCF for missing post-baseline values
ESR (mm/hr)	Change from baseline of ESR	ITT	Week 2 to Week 16	Summary statistics
				mBOCF for missing post-baseline values
		OLE	Week 16 to Week 104	Summary statistics
				mBOCF for missing post-baseline values
		OLE Switcher	Week 16 (or Switch to IXE) to Week 104	Summary statistics
				mBOCF for missing post-baseline values
Disease flare	Disease flare	ITT	Week 2 to Week 16	Summary statistics
				NRI for missing post-baseline values.

Measure	Variable	Population	Analysis Timepoint	Analysis Method
		OLE	Week 16 to Week 104	Summary statistics
				NRI for missing post-baseline values
PASI	OLE Switcher	OLE Switcher	Week 16 (or Switch to IXE) to Week 104	Summary statistics NRI for missing post-baseline values
	PASI total score	ITT – JPsA patients with baseline psoriatic lesion(s) involving BSA $\geq 3\%$	Week 2 to Week 16	Summary statistics
	Change from baseline in PASI total score	OLE – JPsA patients with baseline psoriatic lesion(s) involving BSA $\geq 3\%$	Week 16 to Week 104	mBOCF for missing post-baseline values
	% Improvement in PASI total score			Summary statistics mBOCF for missing post-baseline values
		OLE Switcher – JPsA patients with baseline psoriatic lesion(s) involving BSA $\geq 3\%$	Week 16 (or Switch to IXE) to Week 104	Summary statistics mBOCF for missing post-baseline values
				Summary statistics mBOCF for missing post-baseline values
LEI	Change from baseline in LEI	ITT with baseline LEI > 0	Week 2 to Week 16	Summary statistics mBOCF for missing post-baseline values
		OLE with baseline LEI > 0	Week 16 to Week 104	Summary statistics mBOCF for missing post-baseline values
		OLE Switcher with baseline LEI > 0	Week 16 (or Switch to IXE) to Week 104	Summary statistics mBOCF for missing post-baseline values

Measure	Variable	Population	Analysis Timepoint	Analysis Method
PK	Trough concentrations of ixekizumab in patients with JIA subtypes of ERA (including JoAS) and JPsA	ITT	Week 0 to Week 16	See Section 6.11
Anti-ixekizumab antibodies	Percentage of patients with anti-ixekizumab antibodies	Safety Population	Week 0 to Week 16	See Section 6.12.12
		OLE Population	Week 16 to Week 104	See Section 6.12.12

Abbreviations: ACR = American College of Rheumatology; BSA = Body Surface Area; CHAQ = Childhood Health Assessment Questionnaire; ERA = Enthesitis-related Arthritis; ESR = Erythrocyte Sedimentation Rate; ITT = intent-to-treat; IXE = ixekizumab; JIA = juvenile idiopathic arthritis; JoAS = Juvenile-onset Ankylosing Spondylitis; JPsA = Juvenile Psoriatic Arthritis; LEI = Leeds Enthesitis Index; mBOCF = Modified Baseline Observation Carried Forward; NRI = Nonresponder Imputation; OLE = open-label extension; PASI = Psoriasis Area and Severity Index; PK = Pharmacokinetics; VAS = Visual Analog Scale.

6.9.3. *Other Secondary Efficacy Analyses*

Other secondary efficacy analyses will be based on each treatment period with the respective population at each visit. A listing of each other secondary efficacy analysis may be provided. The analysis methods and analysis periods are described in [Table RHCG.6.9](#) and [Table RHCG.6.10](#).

Table RHCG.6.9. Description and Derivation of Other Secondary Efficacy Endpoints

Measure	Description	Variable	Derivation/Comment	Imputation Approach if with Missing Components
JIA ACR Responder Index	Juvenile Idiopathic Arthritis American College of Rheumatology (JIA ACR) is comprised of 6 variables: active joint count, limitation of motion joint count, physician global assessment, patient/parent global assessment, Childhood Health Assessment Questionnaire (CHAQ), and acute-phase reactant level (either ESR). JIA ACR _x response is defined as at least $x\%$ improvement from baseline in at least 3 of any 6 variables in the core set, with no more than 1 of the remaining variables worsening by more than $x\%$. x is a number from 0 to 100.	Time to First Juvenile Idiopathic Arthritis American College of Rheumatology (JIA ACR) 30/50/70/90/100 Response	(Date of first JIA ACR _x response in defined treatment period – date of first injection + 1) / 7. If the date of first dosing is missing, the date of randomization is used.	Censoring at time of last available visit using Survival analysis (Kaplan-Meier)
hsCRP (mg/L)	The hsCRP test is a highly sensitive quantification of C-Reactive protein (CRP), an acute-phase protein that increases during inflammation.	Change from baseline of hsCRP	Calculation: Change from baseline: observed lab value at visit minus baseline lab value	Missing if baseline or post-baseline value is missing.
PASI	Psoriasis Area and Severity Index (PASI): For patients with plaque psoriasis, combines assessments of the extent of body-surface involvement in 4 anatomical regions (head and neck, trunk, arms, and legs) and the severity of scaling (S), redness (R), and plaque induration/infiltration thickness (T) in each region, yielding an overall score of 0 for no psoriasis to 72 for the most severe disease (Fredriksson and Pettersson 1978). Severity is rated for each index	PASI 75	A clinically meaningful response; at least a 75% improvement in PASI score from baseline.	Missing if baseline or observed value is missing

Measure	Description	Variable	Derivation/Comment	Imputation Approach if with Missing Components
	
(R, S, T) on a 0-4 scale (0 for no involvement up to 4 for severe involvement):
 
 0 = none 1 = slight 2 = moderate 3 = severe 4 = very severe 
The body is divided into 4 anatomical regions comprising the head (h), upper limb (u), trunk (t), and lower limb (l). In each of these areas, the fraction of total BSA affected is graded on a 0-6 scale (0 for no involvement; up to 6 for 90% to 100% involvement):
 
 0 = 0% (clear) 1 = >0% to <10% 2 = 10% to <30% 3 = 30% to <50% 4 = 50% to <70% 5 = 70% to <90% 6 = 90% to 100% 
The various body regions are weighted to reflect their respective proportion of BSA.
			
		PASI 90	Higher level of clearance; at least a 90% improvement in PASI score from baseline.	Missing if baseline or observed value is missing
		PASI 100	Complete resolution of plaque psoriasis; a 100% improvement in PASI score from baseline.	Missing if baseline or observed value is missing

Measure	Description	Variable	Derivation/Comment	Imputation Approach if with Missing Components
LEI	For patients with enthesitis, an assessment that consists of 18 enthesal points is performed by site personnel. The Leeds Enthesitis Index (LEI) has been developed specifically for use in PsA and measures enthesitis at 6 sites (lateral epicondyle [left and right], medial femoral condyle [left and right], and Achilles tendon insertion [left and right]) (Healy and Helliwell 2008).	LEI resolution	Post baseline LEI = 0	If one or more sites are missing, then set to missing. Missing if baseline or observed value are missing
BSA	Percentage of Body Surface Area (BSA): The investigator will evaluate the percentage involvement of psoriasis on each patient's BSA on a continuous scale from 0% (no involvement) to 100% (full involvement), in which 1% corresponds to the size of the patient's hand (including the palm, fingers, and thumb) (Van Voorhees et al. 2016).	Percentage of BSA Change from baseline in BSA	Range from 0% to 100%. Change from baseline in BSA calculated as: observed BSA – baseline BSA	Missing if observed value is missing Change from baseline in BSA Missing if baseline or observed value is missing
Pain being measured by CHAQ (0-100 mm VAS)	The patient is asked to make a pain assessment due to illness. The question uses a 0 to 100 mm VAS where 0 = "no pain" and 100 = "very severe pain"	Change from baseline in Pain VAS	Calculation: Change from baseline: observed score at visit minus baseline score	Missing if post-baseline value missing. Missing if baseline or post-baseline value is missing.

Abbreviations: hsCRP = high-sensitivity C-reactive protein; ESR = erythrocyte sedimentation rate; PsA = psoriatic arthritis; VAS = Visual Analog Scale.

Table RHCG.6.10. Description of Analysis Period and Analysis Method of Other Secondary Efficacy Endpoint

Measure	Variable	Population	Analysis Timepoint	Analysis Method
JIA ACR response	Time to First Juvenile Idiopathic Arthritis American College of Rheumatology (JIA ACR) 30/50/70/90/100 Response	ITT	Week 0 to Week 16	For time to event, Kaplan-Meier
hsCRP (mg/L)	Change from baseline of hsCRP	ITT	Week 2 to Week 16	Summary statistics mBOCF for missing post-baseline values
		OLE	Week 16 to Week 104	Summary statistics mBOCF for missing post-baseline values
	OLE Switcher	OLE Switcher	Week 16 (or Switch to IXE) to Week 104	Summary statistics mBOCF for missing post-baseline values
PASI	PASI 75/90/100	ITT – JPsA patients with baseline psoriatic lesion(s) involving BSA $\geq 3\%$	Week 2 to Week 16	Summary statistics NRI for missing post-baseline values.
		OLE – JPsA patients with baseline psoriatic lesion(s) involving BSA $\geq 3\%$	Week 16 to Week 104	Summary statistics NRI for missing post-baseline values
		OLE Switcher – JPsA patients with baseline psoriatic lesion(s) involving BSA $\geq 3\%$	Week 16 (or Switch to IXE) to Week 104	Summary statistics NRI for missing post-baseline values
LEI	Proportion of patients with complete resolution in enthesitis (LEI score = 0)	ITT with baseline LEI > 0	Week 2 to Week 16	Summary statistics NRI for missing post-baseline values.
		OLE with baseline LEI > 0	Week 16 to Week 104	Summary statistics NRI for missing post-baseline values
		OLE Switcher with baseline LEI > 0	Week 16 (or Switch to IXE) to Week 104	Summary statistics NRI for missing post-baseline values

Measure	Variable	Population	Analysis Timepoint	Analysis Method
BSA	Percentage of BSA	ITT population with baseline plaque psoriasis	Week 2 to Week 16	Summary statistics
	Change from baseline in BSA			mBOCF will be applied for post baseline missing values
		OLE population with baseline plaque psoriasis	Week 16 to Week 104	Summary statistics mBOCF for missing post-baseline values
Pain being measured by CHAQ (0-100 mm VAS)		OLE Switcher population with baseline plaque psoriasis	Week 16 (or Switch to IXE) to Week 104	Summary statistics mBOCF for missing post-baseline values
	Change from baseline in Pain VAS	ITT	Week 2 to Week 16	Summary statistics mBOCF for missing post-baseline values
		OLE	Week 16 to Week 104	Summary statistics mBOCF for missing post-baseline values
		OLE Switcher	Week 16 (or Switch to IXE) to Week 104	Summary statistics mBOCF for missing post-baseline values

Abbreviations: BSA = body surface area; CHAQ = Childhood Health Assessment Questionnaire; hsCRP = high-sensitivity C-reactive protein; ITT = intent-to-treat; IXE = ixekizumab; JIA ACR = Juvenile Idiopathic Arthritis American College of Rheumatology; JPsA = juvenile psoriatic arthritis; LEI = Leeds Enthesitis Index; mBOCF = Modified Baseline Observation Carried Forward; NRI = Nonresponder Imputation; OLE = open-label extension; PASI = Psoriasis Area and Severity Index; VAS = Visual Analogue Scale.

6.9.4. *Exploratory Analyses*

Exploratory efficacy analyses will be based on each treatment period with the respective population at each visit. A listing of each exploratory efficacy analysis may be provided. The analysis methods and analysis periods are described in [Table RHCG.6.11](#) and [Table RHCG.6.12](#).

Table RHCG.6.11. Description and Derivation of Exploratory Efficacy Endpoints

CCI

CCI

CCI

CCI

CCI

CCI

CCI

CCI

Table RHCG.6.12. Description of Analysis Period and Analysis Method of Exploratory Efficacy

CCI

CCI

CCI

CC|

CCI

6.9.5. Sensitivity Analyses

Juvenile idiopathic arthritis ACR30 up to Week 16 will be analyzed based on the ITT Population using the mNRI method, as described in Section 6.3.4. Bayesian analysis will be performed for JIA ACR30 at Week 16.

Sensitivity analyses will be performed as deemed appropriate.

6.10. Health Outcomes/Quality-of-Life Analyses

Health Outcomes analyses will be based on each treatment period with the respective population at each visit. A listing of each health outcome analysis may be provided. See [Table RHCG.6.7](#) and [Table RHCG.6.11](#) for analysis of CHAQ and EQ-5D-Y, respectively. For description of analysis period and analysis methods of CHAQ and EQ-5D-Y, see [Table RHCG.6.8](#) and [Table RHCG.6.12](#), respectively.

6.11. Pharmacokinetic/Pharmacodynamic Analyses

Observed ixekizumab serum trough concentrations will be summarized by time point across the study. Data may also be summarized by weight category, disease, and age as deemed appropriate.

In addition, the clearance of ixekizumab in this patient population may be determined using population PK methods. If this analysis is conducted, then the data from this study may be combined with data from prior studies to aid in model development.

The exposure-response relationship will be investigated between steady-state trough concentrations of ixekizumab and JIA ACR 30 response at Week 16 using graphical methods and, if appropriate, modeling methods. Evaluation of additional time points or endpoints may also be considered.

If applicable, the potential impact of immunogenicity on ixekizumab exposure may be evaluated by graphical assessments, as appropriate, to compare drug exposure between antidrug antibody-(ADA-) negative and treatment-emergent- (TE-) ADA-positive patients at corresponding visits.

Additional analyses may be performed upon receipt of the data. More details of the pharmacokinetic/pharmacodynamic (PK/PD) analyses can be found in a separate PK/PD analysis plan.

6.12. Safety Analyses

The planned safety analyses are consistent with compound-level standards, which are based on various sources, including company standards, internal and external subject matter experts, and cross-industry. Descriptions of the safety analyses are provided in this statistical analysis plan (SAP).

Safety will be assessed by summarizing and analyzing adverse events (AEs), laboratory analytes, including neutrophil counts and immunogenicity, vital signs, Children's Depression Inventory 2

(CDI-2) and Columbia Suicide Severity Rating Scale (C-SSRS). The duration of dosing exposure will also be summarized.

For the OLT Period, the safety data will be summarized and analyzed for the Safety Population for each treatment arm.

For the OLE Period, the select safety data will be summarized and analyzed for the OLE period before the switch, and OLE period after the switch with the corresponding analysis populations. The mean change of the continuous safety measures will be summarized by visits.

For patients who switched to ixekizumab on or after Week 16, categorical safety data after switch of treatment will be summarized with incidence rates by initially assigned treatment group for the Switcher Population (that is, TEAEs, serious adverse events [SAEs], AEs as reason for study treatment discontinuation, treatment-emergent clinical laboratory assessments, treatment-emergent vitals).

For the LTE Period, the safety data will be summarized and analyzed for the LTE Safety Population. For the PTFU Period, the select safety data will be summarized and analyzed for the PTFU Period Population. Summaries of safety data collected during the Post-Treatment Follow-up Period will be presented separately by treatment, according to last treatment received before entering PTFU period. Unless otherwise specified, the Post-Treatment Follow-up Period baseline is defined as the last nonmissing assessment on or prior to the Week 104 (Visit 29) or ETV. The categorical safety measures will be summarized with incidence rates. The mean change of the continuous safety measures will be summarized by visits.

The detail of each population is defined in Section 6.1.1.

Safety topics that will be addressed include the following: AEs, SAE, clinical laboratory evaluations, vital signs and physical characteristics, safety in special groups and circumstances, including adverse events of special interest (AESI) (see Section 6.12.11).

Unless otherwise specified, by-visit summaries will include planned on-treatment visits. For tables that summarize events (such as AEs, categorical lab abnormalities, shift to maximum value), post-last dose follow-up data will be included. Listings will include all safety data.

For selected safety assessments, descriptive statistics may be presented for the last measure observed during post-treatment follow-up (up to 30 days after the last dose of treatment, regardless of treatment period).

6.12.1. Extent of Exposure

Duration of exposure to study treatment (defined as time since first injection of study treatment in days) will be summarized by treatment group during the OLT Period and the OLE Period.

The duration of exposure during the **OLT Period for the Safety Population** will be calculated as:

(Date of last study visit in OLT Period – Date of first injection of study treatment + 1)

The duration of exposure on initially assigned treatment for the **OLE Period Population** will be calculated as:

Date of last visit on initially assigned treatment – Date of first dose in OLE Period + 1

The duration of exposure during the **OLE Period** for the OLE Switcher Population will be calculated as:

(Date of last study visit in OLE Period – The first date of switch to ixekizumab + 1)

The duration of exposure during the **LTE Period** for LTE Safety population will be calculated as:

(Date of last study visit in LTE Period – Date of first injection of study treatment + 1)

Descriptive statistics will be provided for patient days of exposure and the frequency of patients falling into the following different exposure ranges (that is, only the exposure ranges that fall within the treatment period will be presented) will be summarized:

- $>0, \geq 7 \text{ days}, \geq 14 \text{ days}, \geq 30 \text{ days}, \geq 60 \text{ days}, \geq 90 \text{ days}, \geq 120 \text{ days}, \geq 183 \text{ days}, \geq 365 \text{ days.}$
- $>0 \text{ to } <7 \text{ days}, \geq 7 \text{ to } <14 \text{ days}, \geq 14 \text{ to } <30 \text{ days}, \geq 30 \text{ to } <60 \text{ days}, \geq 60 \text{ to } <90 \text{ days}, \geq 90 \text{ to } <120 \text{ days}, \geq 120 \text{ to } <183 \text{ days}, \geq 183 \text{ to } <365 \text{ days}, \geq 365 \text{ days.}$

Overall exposure for each treatment group within the OLT Period and the OLE Period for respective populations will also be summarized in total patient years. This will be calculated as follows:

Exposure in patient years = Sum of duration of exposure with the defined treatment period (for all patients in treatment group) / 365.25.

A listing of study drug exposure will also be provided.

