10.3.1.4. General Considerations for the Post-Treatment Follow-up (PTFU) Period

For the safety analyses during the PTFU period, baseline is defined as the last non-missing assessment on or prior to entering the PTFU period, that is, on or prior to Week 104 (Visit 29), or ETV.

Safety data will be summarized using descriptive statistics without inferential statistics by the study treatment the participant was receiving prior to entering PTFU period. Safety baseline is defined as the last available value immediately before entering PTFU period.

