6.1.2.3. General Considerations for the LTE Period

The LTE period starts at the first injection of ixekizumab at Week 104 (Visit 29) and ends after the injection of ixekizumab at Week 264 (Visit 69) or at ETV (between Weeks 104 and 264).

All safety data will be descriptively summarized using the LTE safety population. For safety analyses using a baseline period, the baseline period is defined as the time from Visit 1 to date/time of the first injection in the LTE period.

Efficacy and health outcomes data collected in the LTE period will be summarized for the ITT population who entered the LTE period without inferential statistics.

All safety data will be descriptively summarized using the LTE safety population, defined as ITT participants who receive at least 1 dose of ixekizumab in the LTE period.

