6.1.2.4. General Considerations for the PTFU Period

For the safety analyses during the PTFU period, baseline is defined as the last nonmissing assessment on or prior to entering the PTFU period, that is, on or prior to Week 104 (Visit 29), or ETV.

Safety data will be summarized using descriptive statistics without inferential statistics by the study treatment the patient was receiving immediately prior to entering PTFU period.

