6.12.2. Adverse Events

6.12.2.1. Analysis of Adverse Events

Adverse events are classified based on MedDRA. A TEAE is defined as an event that first occurred or worsened in severity after baseline and on or prior to the date of the last visit within the treatment period. Both the date/time of the event and the date/time of the dose (that is, injection) are considered when determining TEAEs. The MedDRA Lowest Level Term (LLT) will be used in the treatment-emergent computation. The maximum severity for each LLT during the baseline period will be used as baseline severity (in some cases baseline period is a single time point). Events with a missing severity during the treatment period will be considered treatment emergent. The treatment period will be included as post-baseline for the analysis. If an event is pre-existing during the baseline period but it has missing severity, and the event persists during the treatment period, then it will be considered as treatment-emergent, regardless of the post-baseline level of severity. Adverse events with a particular LLT will be classified as treatment-emergent if they first start on or after the first dose date in the treatment period (i.e., a

patient has no pre-existing conditions with that LLT), or if the severity is greater than the pre-treatment severity for that LLT.

A follow-up emergent adverse event (FEAE) is defined as an event that first occurred or worsened in severity after the date of Week 104 (Visit 29) or the ETV. The MedDRA LLT will be used when classifying FAEs as follow-up emergent. For AEs that are ongoing at the date of Week 104 (Visit 29) or ETV, the maximum severity recorded for each LLT on the date of Week 104 (Visit 29) or ETV will be used as the follow-up baseline severity for that lowest level term.

An overview table will be provided and will include the frequency and percentage of patients who experienced a TEAE, TEAE by maximum severity, a treatment-emergent AESI, SAE, died, or discontinued from the study due to an AE (including death) will be summarized by treatment group for each treatment period. A listing will be provided as well.

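### Two date anchors in the extension safety analyses are wrong as written: LTE exposure is counted from Week 0, and the follow-up baseline for LTE completers is set at Week 104

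*SAP*

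**What the plan says.** **Exposure.** SAP 6.12.1 gives four duration formulas. The OLE formula subtracts "Date of first dose in OLE Period + 1", and the switcher formula starts at the date of the switch to ixekizumab. The LTE formula is "Date of last study visit in LTE Period – Date of first injection of study treatment + 1"; its start term is the one used in the OLT formula. SAP 6.1.2.3 states "The LTE period starts at the first injection of ixekizumab at Week 104 (Visit 29"). Overall exposure for each treatment group "within the OLT Period and the OLE Period for respective populations will also be summarized in total patient years"; the LTE is not named there.

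**Follow-up baseline.** SAP 6.1.2.4 takes the last non-missing assessment at or before entry to the PTFU period and then glosses it: "that is, on or prior to Week 104 (Visit 29), or ETV". SAP 6.12 repeats the gloss as the rule: "the Post-Treatment Follow-up Period baseline is defined as the last nonmissing assessment on or prior to the Week 104 (Visit 29) or ETV". Protocol 10.3.1.4 carries the same Week 104 gloss and also says "Safety baseline is defined as the last available value immediately before entering PTFU period".

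**Follow-up emergent adverse events (FEAEs).** SAP 6.12.2.1 has an FEAE "defined as an event that first occurred or worsened in severity after the date of Week 104 (Visit 29) or the ETV", with baseline severity for ongoing events taken on that same date.

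**PTFU population.** SAP Table RHCG.6.1 and Protocol Table RHCG.10.1 restrict the set to randomized participants with at least one dose and analyse them by assigned treatment. SAP 6.1.2.4 and 6.12 summarise by the last treatment received.

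**The concern.** Long-term safety and tolerability belong to the LTE secondary objective, so its exposure and follow-up tables will be read closely. Followed literally, the exposure formula gives a wrong LTE duration for every participant. It also credits those who stayed on adalimumab until Week 104 with two years before their first ixekizumab injection. The follow-up anchor would compare an LTE completer's PTFU laboratory values, which SAP 6.12.4 plans to summarise, with values about three years old. Protocol Appendix 3 itself notes that laboratory normal ranges in these children vary with age and sex. A programmer must either follow the text and produce the wrong figure, or correct it without documentation.

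**Working it through.** **Inputs.** From the protocol's Schedule of Activities: Week 0 = Day 0, Week 104 (Visit 29) = Day 728, Week 108 (Visit 30) = Day 756, Week 264 (Visit 69) = Day 1848. PTFU visits 802 and 803 fall 8 and 12 weeks after the last visit.

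**Check of the plan's own figures.** LTE length = 264 − 104 = 160 weeks and OLE length = 104 − 16 = 88 weeks. Both match the Protocol synopsis.

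**Exposure, literal formula against LTE-only formula.**
- Completer, literal: 1848 − 0 + 1 = 1849 days. LTE only: 1848 − 728 + 1 = 1121 days. Ratio 1849/1121 = 1.65.
- Last visit at Week 108, literal: 756 − 0 + 1 = 757 days. LTE only: 756 − 728 + 1 = 29 days. Ratio 757/29 = 26.1.
- The excess is 728 days in every case. The shortest possible literal value is 728 + 1 = 729 days, so everyone falls in the ≥365-day category. LTE-only exposure reaches 365 days only at Week 156 (1092 − 728 + 1 = 365).

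**Follow-up anchor for an LTE completer.**
- Lag from the named anchor to the end of the LTE: 1848 − 728 = 1120 days = 160 weeks; 1120/365.25 = 3.07 years.
- FEAE window as written: Week 104 to Week 272 (264 + 8) or Week 276 (264 + 12). That is 168 or 172 weeks, of which 160 are LTE treatment.

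**The conflicting texts side by side.**
- Week 104 or early termination: the gloss in SAP 6.1.2.4, SAP 6.12, SAP 6.12.2.1, and the first paragraph of Protocol 10.3.1.4.
- Entry to follow-up, or the last treatment-period visit: the opening phrase of SAP 6.1.2.4, the last sentence of Protocol 10.3.1.4, the follow-up emergent SAE definition in SAP 6.12.3.2, and the neutrophil follow-up set in SAP 6.12.4.2.
- Both at once: the PTFU bullet in SAP 5.1, where the Week 104 anchor and the last regularly scheduled visit stand in one unfinished sentence.

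The two groups agree for participants who stop at Week 104 and disagree for LTE completers.

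**The case against.** The strongest reply is that intent is plain. The exposure line is labelled as LTE, SAP 6.1.2.3 fixes the LTE start, and SAP 6.12.1 shows only the exposure ranges that fall within the treatment period. For follow-up, the governing phrase comes first in SAP 6.1.2.4, Protocol 10.3.1.4 repeats it, LTE early leavers can use the early-termination branch, and SAE and neutrophil analyses already use a sound anchor. SAP 6.12.2.1 also bars an event already counted as treatment-emergent from being counted again as an FEAE. All of this stands, and it keeps the severity low. It does not make the stated rules correct. The double-counting guard does nothing for the laboratory baseline. SAP 5.1 does write Visit 69 and ETV together, but the protocol's schedule gives them separate columns, and a Week 264 completer has not terminated early.

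Several stronger readings are tempting and are not supported:
- **LTE patient-years or exposure-adjusted rates are inflated.** SAP 6.12.1 plans patient-year totals only for the OLT and OLE. The antibody-related event rates in SAP 6.12.12.2.3 use time in antibody status, not this formula.
- **About 60 of 100 participants drop out of the PTFU set.** Read literally, the word randomized would exclude the assigned cohort. But Protocol 5.1 and 5.1.2 use random-allocation language for everyone, so this is loose wording. The real remainder is the clash between grouping by assigned and by last treatment, for example for an adalimumab participant who switched and left during the OLE.
- **The LTE safety baseline, running from Visit 1 to the first LTE injection, is a defect.** It does mean that a same-severity recurrence may not count as LTE treatment-emergent. But it is prespecified, identical in SAP 6.1.2.3 and Protocol 10.3.1.3, and parallel to the OLE rule in SAP 6.1.2.2.1. Any size put on the effect would rest on event rates that the documents do not give. It is a trade-off.
- **All of this is text left over from before the LTE.** That fits only the Week 104 anchors. The SAP revision history shows that the LTE exposure formula was added for the LTE.

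**Conclusion.** Two rules give wrong results if followed as written. LTE exposure is overstated by 728 days per participant, a factor of 1.65 for a completer and 26.1 for someone leaving at Week 108. The PTFU baseline and FEAE anchor are 1120 days too early for LTE completers and conflict with other text in both documents. The PTFU population wording is an editorial point. The figures use scheduled visit days, ignore the ±7-day windows, and assume the first injection at Week 0 and the first LTE injection at Week 104. Every affected output is a descriptive safety summary; the Week 16 primary analysis and the futility rule do not depend on any of this. Severity: minor.

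**What to change.** - **SAP 6.12.1:** LTE exposure = date of last LTE visit − date of first injection in the LTE period + 1.
- **SAP 6.1.2.4, 6.12 and 6.12.2.1, and Protocol 10.3.1.4:** anchor the PTFU baseline, the FEAE definition and the FEAE baseline severity at the last treatment-period visit before PTFU (Week 104 for those not entering the LTE, Week 264 for LTE completers) or the early termination visit.
- **SAP 5.1:** repair the PTFU sentence that carries both anchors.
- **SAP Table RHCG.6.1 and Protocol Table RHCG.10.1 (editorial):** define the PTFU population as treated participants, randomized or assigned, who entered PTFU, and state one grouping rule that agrees with SAP 6.1.2.4 and 6.12.

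The cost is wording in the SAP and matching text in two protocol sections. No new data, visits or analyses are needed, and the cumulative LTE safety baseline can stay as it is.
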